9.4 Medical Monitoring

It is the responsibility of the Principal Investigator to oversee the safety of the study. This safety monitoring will include careful assessment and appropriate reporting of AEs as noted above, as well as the construction and implementation of a study management plan. Please see [Section 11](#) for more information. Medical monitoring will include a regular assessment of the number and type of SAEs.

9.5 Interim Analysis

An interim analysis will be performed on the primary endpoint when 30% of eligible patients have been enrolled and have completed the 6 months follow-up. The interim analysis will be performed by an independent statistician who is blinded for the subjects' treatment allocation.

Some of the questions that will be evaluated during the interim analysis will include:

- Is there an unexpectedly high rate of severe or life-threatening adverse events?
- Is the outcome of the trial treatment comparable with that of previous studies?

- Do the results of the interim analysis prove statistically significant differences between the trial treatments that exceed the differences defined by the statistical guidelines of the trial?

10 Data Handling and Record Keeping

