3.1 Primary Endpoint

The primary endpoint of this study is to evaluate the proportion of patients reaching target levels (8-10 ng/ml) on Day 3 and Day 7 after kidney transplantation.

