4.4 Genotyping and Dosing Administration

The *CYP3A5* 6986A>G (rs776746) variant is ideal for a pharmacogenomic study as it has a high estimated allele frequency across various populations, including Whites (82% to 95%), Japanese (85%), Southeast Asians excluding Japanese and Chinese (67%), Chinese (65%), Pacific Islanders (65%), Southwest American Indians (40%), and African Americans (33%) (Lamba, 2012). At the UNC-CH multidisciplinary kidney transplantation team, we see approximately 80 patients for kidney transplantation per year. Of those 80 patients, approximately 60% are Whites and 40% are African Americans. We therefore expect that the *CYP3A5* 6986A>G (rs776746) variant will be relatively frequent in our study population. In addition, to be able to effectively compare outcomes between expressers and nonexpressers as well as between genotyped and nongenotyped subjects, we will make every effort to enroll African Americans to the study so as to get equal numbers of Caucasians and African Americans in our study.

At study enrollment, buccal swab samples will be obtained for genotyping of the *CYP3A5* 6986A>G (rs776746) variant. Based on the genotyping result, patients will be categorized into two categories:

- *CYP3A5* expressers (*CYP3A5**1/*3 and *CYP3A5**1/*1)
- *CYP3A5* nonexpressers (*CYP3A5**3/*3)

Patients will then receive the initial tacrolimus dose based on the genotype-guided dosing algorithm outlined in [Section 6.2.1](#). Subsequent tacrolimus dosing will then be adjusted according to trough concentrations and therapeutic target concentrations.

5 Subject Selection and Withdrawal

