5.4 Removal of Patients from the Genotype-guided Tacrolimus Therapy

Removal of patients from the genotype-guided tacrolimus therapy can occur for the following reasons:

- 1) Extraordinary medical circumstances: If, at any time the constraints of this protocol are detrimental to the patient's health, then the patient may be removed from the genotype-guided tacrolimus therapy. In this event, the investigator will do the following:
 - Notify the UNC-CH Principal Investigator
 - Document the reason(s) for withdrawal on flow sheets or Case Report Form (CRF)

- Notify the IRB

- 2) Voluntary withdrawal
- 3) Excessive toxicity: Patients who experience any grade III or grade IV AE deemed by the Principal Investigator to be related to tacrolimus therapy
- 4) Investigator's judgment: When deemed in the best interest of the patient by their attending physician, patients should be removed from the study and included in the intent-to-treat (ITT) analysis.
- 5) Premature closure of the study: This study may be prematurely terminated, if in the opinion of the investigator there is sufficient reasonable cause. Written notification documenting the reason for study termination will be provided by the investigator.
- 6) Circumstances that may warrant termination include, but are not limited to:
 - Determination of unexpected, significant, or unacceptable risk to patients
 - Failure to enter patients at an acceptable rate
 - Insufficient adherence to protocol requirements
 - Insufficient complete and/or evaluable data

6 Study Drug

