8.2 Sample Size Determination

The primary endpoint of this study is to evaluate the proportion of patients reaching target levels (8-10 ng/ml) on day 3 and day 7 after kidney transplantation.

We calculated that a total study population of 260 patients (pharmacogenomics group = 130; control group = 130 patients) would be sufficient to provide a statistical power of 90% to detect a significant difference between the two groups, on the basis of a two-sided χ^2 test, a significance level of 5%, a frequency of approximately 50% for the *CYP3A5*3/*3* genotype, and a 40% and 60% frequency of the primary endpoint in the control and pharmacogenomic group (Thervet et al. 2010), respectively. Because of the nature of the study design we anticipate a small rate of sample dropout (<5%), which should not appreciably impact the power of the study.

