Statistical testing, whenever performed, will be 2-sided with a significance (alpha) level of 0.05. In addition, 95% confidence intervals will also be determined. All statistical analyses will be conducted using SAS® or other appropriate statistical programs.

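### Section 9.5 plans an interim significance assessment of the primary endpoint with no boundary; if a significant interim result can support a claim or an early stop, type I error is about 9% at 39 v 39, not 5%

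*Combined protocol and SAP*

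**What the plan says.** All references are to the combined protocol and SAP.

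- Section 9.5 sets the timing and endpoint: "An interim analysis will be performed on the primary endpoint when 30% of eligible patients have been enrolled" and have been followed for 6 months.
- One of the three example questions listed there is whether the interim results "prove statistically significant differences between the trial treatments that exceed the differences defined by the statistical guidelines of the trial". It stands beside a question on severe adverse events and one on comparability with previous studies.
- Section 8.3 gives the only significance rule: "Statistical testing, whenever performed, will be 2-sided with a significance (alpha) level of 0.05".
- Section 8.2 states that 130 patients per group "would be sufficient to provide a statistical power of 90% to detect a significant difference between the two groups", using a two-sided chi-square test at 5% and endpoint rates of 40% v 60%. It does not mention an interim look.
- Section 5.4 allows premature closure at the investigator's discretion. It names risk to patients, slow entry, poor adherence and insufficient data, introduced by "Circumstances that may warrant termination include, but are not limited to". Efficacy is not named.

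**The concern.** Section 9.5 judges an interim between-group difference on the confirmatory endpoint against guidelines that appear nowhere in the documents. There is no interim boundary, no alpha spending, no adjusted final level and no efficacy stopping rule. A statistician who has to run this analysis would fall back on the 0.05 default in Section 8.3, and the final test would then use 0.05 again.

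Section 9.5 also does not say what follows a significant result. If that result could be reported as a positive finding, or could lead to early closure for efficacy, the primary comparison would have two chances to reject at 0.05 each. The 5% level on which Section 8.2 rests would then not hold. Timing matters too, because a boundary chosen after the interim comparison has been seen does not protect the error rate.

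**Working it through.** **Inputs from the documents.** Two-sided alpha 0.05 (8.2, 8.3); rates 40% and 60%, 130 per group, power 90% (8.2); one interim at 30% (9.5). 30% of 260 is 78 patients, or 39 v 39 if the groups fill equally. That balance is an assumption.

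**1. Reproduce the plan's figure.** Pooled-variance chi-square, no continuity correction:

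n = [1.96 × sqrt(2 × 0.5 × 0.5) + 1.2816 × sqrt(0.4 × 0.6 + 0.6 × 0.4)]² / 0.20² = (1.3859 + 0.8879)² / 0.04 = 129.3, so 130 per group.

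Power at 130 is 90.2%. The plan's 260 is therefore the single-look sample size, with all of the 5% spent at the end.

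**2. Information at the interim.** t = (2/130) / (1/n1 + 1/n0).

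- 39 v 39: 0.01538 / 0.05128 = 0.30.
- 39 v all 130 controls (if the retrospective controls are already complete): 0.01538 / 0.03333 = 0.46.

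**3. Two looks at two-sided 0.05.** Under no difference, the interim and final Z are bivariate normal with correlation sqrt(t). Overall error = 1 − P(|Z1| < 1.96 and |Z2| < 1.96).

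| Information fraction t | Overall type I error |
|---|---|
| 0.25 | 9.1% |
| 0.30 (39 v 39) | 8.9% |
| 0.40 | 8.6% |
| 0.46 (39 v 130) | 8.4% |
| 0.50 | 8.3% |
| 0.60 | 8.0% |

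**4. Check by simulation.** One million trials per null rate, uncorrected chi-square, 39 v 39 and then 130 v 130.

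| Null rate | Final test alone | Either look |
|---|---|---|
| 40% | 5.0% | 9.0% |
| 50% | 5.4% | 9.6% |

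The excess due to the interim look is about 4 points in both rows. The higher total at 50% partly reflects the discreteness of the final test itself.

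**5. Does a minimum difference help?** The only between-group difference in the plan is the 20 points in Section 8.2. Suppose, as an assumption, that the undefined differences in Section 9.5 mean those 20 points and must be reached as well as p<0.05.

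- 39 v 39: p<0.05 already needs 1.96 × sqrt(2 × 0.25 / 39) = 0.222 at a pooled rate of 50%, or 0.217 at 40%. That is about 22 points, so the extra condition changes nothing and 8.9% stands.
- 39 v 130: p<0.05 needs 1.96 × sqrt(0.25 × 0.03333) = 0.179, about 18 points. The 20-point condition then matters, and the error falls to between 6.5% and 6.8%.

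**6. Cost of a boundary.** With interim p<0.001 and final p<0.0495, overall error is 5.00% at t = 0.30 and 4.98% at t = 0.46. Power at 130 per group is 90.17% at a final level of 0.05 and 90.09% at 0.0495.

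**The case against.** The strongest reply is that the plan never attaches a consequence to the interim question. Section 9.5 lists it as something to evaluate, and none of the closure reasons named in Section 5.4 is efficacy. If only the final test can support a claim, the level is 5% and nothing is inflated. This stands. A reader might infer that the trial has a 9% error rate, or that it permits stopping for efficacy, and the documents establish neither. They also do not exclude it: the list in Section 5.4 is open-ended, and the question is worded as whether the results prove a difference.

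A second reply is that Section 9.5 asks for more than p<0.05, since the difference must also exceed a defined amount. That amount is not given. The 20-point reading gives no protection at 39 v 39, although it does help if all the controls are in.

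Two other stronger readings should be set aside. A reader might take 8.9% as a ceiling. It is not: simulation reaches 9.6%, and if the 78 patients filled unevenly, say 10 v 68 (t = 0.13), the normal approximation gives 9.4%. A reader might also see a contradiction in a statistician blinded to allocation comparing the groups. Coded group labels make that workable, so there is no error there.

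Finally, this is an open-label, single-centre study with largely historical controls, so confounding may well matter more than a few points of alpha. That bears on how serious the gap is. It does not restore a 5% level that the plan itself adopts.

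**Conclusion.** The gap is real. The plan contains an interim significance question on the primary endpoint, a reference to guidelines that do not exist in the documents, and a 0.05 default that would otherwise apply at both looks.

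Its effect is conditional. If an interim p<0.05 can support a claim or an early stop, overall type I error is about 9% at 39 v 39 (8.9% analytic, 9.0% to 9.6% simulated) and about 8.4% with all 130 controls available. If only the final test counts, it is 5%. The excess is therefore roughly 0 to 4 points. These figures assume 30% of 260 patients, balanced filling except where stated, and rejections counted in either direction.

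This should be fixed before the interim comparison. Because the consequence is unstated and the excess is conditional, it does not by itself undermine the design.

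**What to change.** Before any interim outcome comparison, amend Section 9.5 to remove the reference to statistical guidelines or to define them, and choose one of two routes.

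(a) State that the interim is limited to safety and feasibility, or that any between-group efficacy comparison is descriptive and cannot support a claim or an early stop for efficacy. One sentence is enough. The final level stays at 0.05 and power at 90.2%.

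(b) Keep the test and set a boundary, for example Haybittle-Peto with interim p<0.001 and final p<0.0495. Exempt it from the 0.05 default in Section 8.3, state the final level in Section 8.2, and say which patients and which controls enter the interim and what crossing the boundary would lead to. Power goes from 90.2% to 90.1%, with no added patients.

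Either route costs protocol wording only. Route (a) is the simpler if no early efficacy decision is intended.

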10.1 Confidentiality

Information about study subjects will be kept confidential and managed according to HIPAA requirements of 1996. Those regulations require a signed subject authorization informing the subject of the following:

- What protected health information (PHI) will be collected from subjects in this study
- Who will have access to that information and why
- Who will use or disclose that information
- The rights of a research subject to revoke their authorization for use of their PHI.

In the event that a subject revokes authorization to collect or use PHI, the investigator, by regulation, retains the ability to use all information collected prior to the revocation of subject authorization. For subjects that have revoked authorization to collect or use PHI, attempts should be made to obtain permission to collect at least vital status (ie, that the subject is alive) at the end of their scheduled study period.

Of major concern to most research participants is the confidentiality of information collected as part of a research study. All information will be kept strictly confidential and used for research purposes only. No identifying information will be disclosed in reports, publications, or presentations.

Procedures to assure confidentiality will be strictly observed. The study will follow standard guidelines to assure that participant confidentiality is maintained. All data will be:

- Kept in confidential locked files;
- Identified by participant identification number (PID) only, which will be generated using random alpha numeric code only; and
- Kept separately from identifying information used for subject tracking and follow-up contacts.

The following methods will be utilized to protect the confidentiality of participant data:

- 1) Data collected at clinical site and entered into the database will contain a PID number that does not reflect any personal information.
- 2) Data linking a participant to a PID number will be stored locally in locked files. This information will not leave the clinical site and will be accessible to clinical site study staff only (but IRB may request access to patients' files during site visits).
- 3) Access to the data will be strictly controlled. User names and passwords will be distributed only to the appropriately trained clinical staff members.
- 4) Specimens collected from participants and transferred to the CGI will be coded for tracking purposes but will not contain any personal identifiers.
- 5) The statistician or the primary person responsible for the data analysis will not receive any original data for auditing or quality assurance purposes that contain any personal identifying information. Any personal identifiers will be completely removed prior to sending the data.

10.2 Records Retention

Methods for record retention are stated in the clinic's SOPs. Government agency regulations and directives require that all study documentation pertaining to the conduct of a clinical trial must be retained by the study investigator. In the case of a study with a drug seeking regulatory approval and marketing, these documents shall be retained for at least two years after the last approval of marketing application in an ICH region. In all other cases, study documents should be kept on file until three years after the completion and final study report of this investigational study.

The patient's confidentiality will be maintained and will not be made publicly available to the extent permitted by the applicable laws and regulations.

10.3 Method of Data Collection

Initially, while kidney transplant recipients receive care in the hospital, all data will be collected from medical and drug records obtained during the inpatient hospitalization. Subsequently, data on clinical, medication use, and environmental factors will be collected post-transplant in the clinic by the renal transplant coordinator who enters the patients' clinical findings, including phone conversations, in EMR.

10.4 Data Obtained for Analysis

10.4.1 Data to be collected

There will be 3 broad categories of data collected 1) patient-specific clinical and environmental data 2) genotype data, and 3) study outcomes. All participants will undergo a baseline interview to collect clinical and environmental data, and buccal swab sample will be collected for DNA extraction, genotyping, and storage for pharmacogenomic studies. At each subsequent visit, participants will undergo a follow-up interview as part of routine care to collect clinical, environmental, and outcome data.

10.4.1.1 Clinical and Environmental Factors

The clinical and environmental factors to be collected will be those that can alter the response to tacrolimus, increase the risk of any of the other study outcomes (eg, graft rejection), and fully describe the patient population and relevant subgroups.

Clinical factors include factors associated with altered tacrolimus dose such as age, sex, pre-existing medical conditions, and body surface area. Environmental factors include interacting medications, smoking, and alcohol use. Interacting medications will include all possible interacting medications and dietary supplements that may alter the PK or pharmacodynamics (PD) of tacrolimus. All information pertaining to clinical and environmental factors can be found in the EMR as it is routinely collected as standard care for kidney transplant recipients.

10.4.1.2 Genetic Data

There will be two types of genetic data: 1) genotype data related to tacrolimus dosing, which includes primary genotype data required for the dosing algorithms and 2) other genetic data that will be used for additional, ancillary analyses. The data unrelated to the dosing algorithms will be derived from the stored buccal swab sample at the Central Laboratory (CL) and are not required for the clinical trial itself. As such, they are not discussed further in this protocol. The first (genotype data required for the dosing algorithm) will be assayed at CGI under the strictest CLIA (Clinical Laboratory Improvement Amendment) standard for genotyping of human specimens. The other genotype/sequencing data will be used to define additional genetic determinants of tacrolimus dosing in patients who have disparate response from the genotype-guided dose.

Genotyping at the Central Laboratory. The CL will be responsible for: 1) extracting DNA from all participants' buccal swab samples and 2) storing DNA on all participants for future genotyping of other variants of other genes that may be important for assessing response to tacrolimus. For future studies, the CL will be responsible for developing a multiplex platform that can assay numerous genetic variants within one reaction.

Sample Collection for Storage and Analyses in Central Laboratory. Following acquisition of informed consent, buccal swab samples will be collected per manufacturer's directions. Using DNA isolation kits suitable for buccal swab samples, DNA will be isolated at the CL according to the manufacturer's instructions. A third of the aliquot will be retained by the CL, and the remainder will be delivered to CGI in a chilled insulated container. The DNA samples will be stored in barcoded tubes at the CL. All DNA samples that will be sent to CGI will also be in barcoded tubes, so that laboratory personnel at CGI are blinded to the patient's identity. All samples will be tracked using the barcode and tracking system.

10.4.2 Historical Data

Historical data from the control group will be obtained from 2010 until the end of study period. The historical controls will consist of age- and disease-matched patients who met eligibility criteria and have had previously

received kidney transplantation with standard tacrolimus dosing. These patients will also be asked to give consent for genotyping during a standard routine follow-up visit post-transplantation. Eligible patients who consented will be included in the control group and their safety and efficacy data will be collected retrospectively for up to 12 months from the initiation of the first tacrolimus dose.

10.4.3 Missing Data

The main problem from missing data will be missing tacrolimus blood levels either from attrition or missed visits. Given that the initial monitoring of tacrolimus (Day 3 and Day 7) for the primary outcome will be conducted at the hospital, we expect the issue of attrition and missing data to be very unlikely. Extensive efforts will be made to collect complete information on each subject enrolled throughout the study. The optimal approach to missing data is to be proactive and be diligent in avoiding it. Additional methods, including calendar alerts, e-mail reminders, and reminder calls may be employed to minimize missed visits.

10.5 Data Management

Using appropriate data management tools such as Research Electronic Data Capture (REDCap), the data management team will develop a data validation plan, rule set specifications, and programming logic to implement data validation rules. The rule set will include checks for missing fields, range checks, skip pattern-logic, and inter and intra form checks. Prior to analysis of the data, the data management team will perform extensive, independent testing of the validation program functionality by entering data known to violate validation rules and determining if the errors are detected.

Data validity will be monitored to address critical missing, inaccurate, illogical, or inconsistent values in the data submitted by the investigator and CL. Rules will be developed and applied to evaluate data in a hierarchical fashion: 1) safety and efficacy; 2) eligibility; 3) analysis and outcome data; and 5) descriptive non-outcome data. Rules will be implemented after the data are committed and are managed via the query tracking system.

11 Study Management

11.1 Study Monitoring Plan

This study will be monitored by the investigator. The investigator will permit study-related monitoring, audits, and inspections by the IRB, government regulatory bodies, and University compliance and quality assurance groups of all study related documents (eg, source documents, regulatory documents, data collection instruments, study data etc.). The investigator will ensure the capability for inspections of applicable study-related facilities (eg, pharmacy, diagnostic laboratory, etc.).

Participation as an investigator in this study implies acceptance of potential inspection by government regulatory authorities and applicable University compliance and quality assurance offices.

